9.1. Blood Sampling and Handling

Blood samples for plasma concentration of study drug and its main metabolite (TV-45065) will be collected 1-2 hours after the dosing and after the ECG is administered as specified in [Table 1](#) (SoA-Main Study). Samples for PK analysis will be analyzed for the concentration of pridopidine and its main metabolite TV-45065 using an appropriate validated method. Incurred sample reanalysis may be performed.

Drug concentration information that would unblind the study will not be reported to investigative sites or blinded study personnel until the study has been unblinded.

Samples for biomarker analysis of biomarker (NfL) will be collected as detailed in [Table 1](#) (SoA-Main Study).

Sampling analyses for DNA extraction will be performed only once during the study, for future genetic analysis related to pridopidine response or HD.

Blood samples will always be collected after the ECG is administered (not before).

9.1.1. PK Analysis

PK assessments include plasma concentration of pridopidine and its main metabolite (TV-45065) at Weeks 26, 52, 65, and 78 and at last participants' visit.

All pridopidine and TV-45065 concentration data will be listed for participant at each visit and timepoint, including date and time of sample collection and elapsed time from last dose.

Descriptive statistics of plasma concentrations of pridopidine and TV-45065 as continuous variables additionally with geometric mean and coefficient of variation (CV) will be presented by treatment groups, scheduled visit and timepoint. For these summaries, values which are below lower limit of quantification (LLOQ) will be treated as zero; if the mean of the numbers is <LLOQ, the value would be reported as "BLQ" (below limit of quantification).

Additional PK samples collected in case of an SAE will be listed but not included in the summaries.

An exposure-response correlation between pridopidine plasma concentrations vs efficacy and safety measures (including QTcF), as well as exploratory analysis and additional covariate analysis may be performed and reported separately as applicable.

Additional PK analyses may be specified in a SAP addendum, or separate SAPs.

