9.4.7. PK Analysis

Descriptive statistics of plasma concentrations of pridopidine and TV45065 as continuous variables additionally with geometric mean and coefficient of variation will be presented by treatment groups, scheduled visit and timepoint.

An exposure-response correlation between pridopidine plasma concentrations vs change from Baseline in efficacy (e.g., UHDRS-TFC) and safety measures (including QTcF), and additional covariate analysis may be performed and reported separately as applicable.

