3. STUDY DESIGN

3.1. General Design and Study Schema

This is a multicenter, randomized, parallel group, double-blind, placebo-controlled study to evaluate the efficacy and safety of pridopidine administered orally at a dose of 45 mg bid versus placebo in treatment of functional impairment in participants with early HD, defined as Stages 1 and 2 based on UHDRS-TFC scores (HD1 is UHDRS-TFC 11-13 and HD2 is UHDRS-TFC 7-10). It is planned to enroll a total of 480 participants (240 participants within each treatment arm).

The study will consist of a screening period, a double-blind treatment period (hereafter referred to as the Main Study) and an OLE as described in study schemas [Figure 1](#)- Main Study and [Figure 2](#)- OLE.

After having signed an informed consent, each participant will be randomized in a 1:1 ratio to the active (pridopidine 45 mg bid) or control (placebo) arm, stratified by Baseline HD stage (HD1 vs. HD2) and Baseline neuroleptic use (Yes/No), for a 65 to 78 weeks double-blinded treatment period as the Main Study.

The Main Study will include an initial 2-week titration period, a 63-week double-blind full-dose maintenance treatment period, followed by a variable double-blind treatment period of up to 13 weeks.

Starting on Day 1, during the titration period, all participants will self-administer 1 capsule of study drug orally, once daily (QD), in the morning for 2 weeks. Thereafter, the study drug will be taken orally bid in the morning and in the afternoon (7-10 hours apart) for 63 weeks (full-dose maintenance double-blind treatment period). Participants who complete the Maintenance period (63 weeks) will continue into a variable double-blind period of up to 13 weeks or until the last participant randomized completes 65 weeks of treatment (2-weeks Titration + 63-weeks full-dose), whichever comes first.

The reason for the variable length double-blind period is because the study will be considered to have completed when the last participant randomized (and who has not discontinued) completes 65 weeks of double-blind treatment. Participants enrolled prior to that in the study will have the opportunity to complete 78 weeks in the Main Study. Participants enrolled towards the end of the study will have completed between 65 and 78 weeks in the Main Study. The primary endpoint is the change from Baseline to Week 65 in UHDRS-TFC. Change from Baseline to Week 52 and 78 in UHDRS-TFC are secondary endpoints, as indicated in the Section 2.

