- o. Single ECG 1-2 hours post-dose.
- p. Single ECG pre-dose.
- q. Only for participants not continuing to Open-label Extension (single ECG). Participants continuing to OLE, will have triplicate ECG (pre-dose) at V8.
- r. Vital signs (body temperature, systolic and diastolic blood pressure, and heart rate) will be measured in a supine position after 5 minutes rest; thereafter, blood pressure should be measured again after standing for 2 minutes.
- s. For training purposes only.
- t. This information will be collected as part of the concomitant medication inquiry.
- u. Blood samples for plasma concentration of study drug will be collected 1-2 hours after dosing and after the ECG. PK samples should not be collected from participants who are off drug and remain in the study.
- v. Always collect blood after ECG is administered (not before).
- w. Sample analysis will be drawn at Screening or Baseline.
- x. Sampling analyses for deoxyribonucleic acid (DNA) extraction will be performed only once during the study, at Screening or at Baseline, for future genetic analysis related to pridopidine response or HD.
- y. Sampling analyses for CAG, only if needed.

Table 2: Schedule of Activities – Open-label Extension

Study Period Procedures and assessments	Open-Label Titration Period		Open-Label Full-dose Treatment Period					Follow-up Safety Assessment	
	Study Clinic Visit	OLE V1 ^a (same as Main Study V8)	OLE V2	OLE V3	OLE V4+	OLE EoS/ET ^b	OLE F/U		
Telephone Call Safety Visit		📞	📞	📞					📞
OLE Study Week	OLE Day 1 (same as Main Study Wk 78/EoS)	OLE Wk 2	OLE Wk 4	OLE Wk 13	OLE Wk 26	OLE Wk 39 & every 26 wks thereafter	OLE Wk 52 & every 26 wks thereafter	X	+2 weeks after OLE EoS/ET
Visit Windows (days)		±1	±5	±5	±14	±14	±14	±14	±5
OLE Informed consent	X (if not obtained at Main Study V7)								
Re-confirm eligibility to OLE	X								
Clinical laboratory tests (serum chemistry, hematology) ^d	X		X		X		X	X	
Urinalysis ^e	X								
Pregnancy test (for WOCBP)	U		U		U		U	U	
Monthly urine pregnancy test (at home)									
Brief physical examination	X (full PE)		X		X		X	X	
12 lead ECG	X ^{f,g}		X ^g		X ^h			X ^h	
Vital signs	X		X		X		X	X	
C-SSRS (since last visit version)	X		X	X	X	X	X	X	X
UHDRS-TFC	X				X		X	X	
UHDRS-TMS	X				X		X	X	
SDMT	X				X		X	X	
SWR	X				X		X	X	
Q-Motor	X		X		X		X	X	
PBA-s (Short Form)	X		X		X	X	X	X	X
CGI-C	X				X		X	X	
HDQoL	X				X		X	X	

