4.1.6. PK Population (PKP)

The PK population (PKP) will include all randomized participants who received at least 1 dose of pridopidine and have at least 1 valid PK assessment. In this population, treatment will be assigned based upon the treatment participants actually received, regardless of the treatment to which they were randomized. This PKP will be used for all PK analyses.

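### SAP 9.1.1 sets values below the LLOQ to zero in the same summaries that report a geometric mean, which is then zero or not computable in any cell with such a value

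*SAP*

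**What the plan says.** SAP 9.1.1 plans descriptive statistics for pridopidine and TV-45065 concentrations, "additionally with geometric mean and coefficient of variation (CV) will be presented by treatment groups, scheduled visit and timepoint". The next sentence ties itself to those same summaries and states that "values which are below lower limit of quantification (LLOQ) will be treated as zero". It adds a display rule: "if the mean of the numbers is <LLOQ, the value would be reported as" BLQ. The text does not say whether that is the arithmetic mean, the geometric mean or both, nor whether the CV is arithmetic or geometric.

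Protocol 9.4.7 plans the same statistics ("Descriptive statistics of plasma concentrations of pridopidine and TV45065 as continuous variables additionally with geometric mean and coefficient of variation will be presented") and has no rule for values below the LLOQ. Neither document gives the geometric mean its own convention: zeros are not excluded, no substitution is named, and no rule for leaving the cell uncalculated is given.

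Two other places bear on how often the case arises. SAP 4.1.6 defines the analysis set: "The PK population (PKP) will include all randomized participants who received at least 1 dose of pridopidine and have at least 1 valid PK assessment". It sets no compliance requirement. Footnote u to SAP Table 1 places the sample 1-2 hours after dosing and says "PK samples should not be collected from participants who are off drug and remain in the study".

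**The concern.** Setting unquantifiable concentrations to zero is workable for an arithmetic mean, SD or median. It does not work for a geometric mean, which needs strictly positive values. Because the zero rule is written for the whole set of summaries, a programmer who follows it cannot produce a meaningful geometric mean in a cell that contains such a value, and would have to choose a remedy that the plan does not state. The geometric mean is the typical-exposure figure that readers would take from this table, so the choice should be made in advance and be visible.

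**Working it through.** The plan gives no figure to reproduce here. The check has three parts.

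**1. Algebra.** For n concentrations x₁…xₙ,

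GM = (x₁ × x₂ × … × xₙ)^(1/n) = exp[(1/n) Σ ln xᵢ].

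If any xᵢ = 0, the product form gives 0 whatever n is. The log form needs ln(0), which does not exist, so software returns 0, a missing value or an error. A CV derived from the SD of the logs fails for the same reason.

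**2. Illustration on assumed data.** The documents give neither the LLOQ nor typical concentrations. The data here are one simulated lognormal sample per cell size (true geometric mean 500, log-SD 0.5, LLOQ 1, arbitrary units), with one value then replaced by a BLQ value.

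| Statistic | n = 20 | n = 200 |
|---|---|---|
| GM, all values quantifiable | 509.5 | 468.0 |
| GM, one BLQ value set to 0 (rule as written) | 0 | 0 |
| GM, quantifiable values only | 505.3 | 466.0 |
| GM, BLQ set to LLOQ/2 | 357.6 | 450.3 |
| GM, BLQ set to LLOQ | 370.2 | 451.9 |

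At n = 200 the arithmetic mean moves only from 528.8 to 523.5 under the zero rule, and the arithmetic CV stays computable (about 0.58). The failure is therefore confined to the geometric mean and any log-based CV.

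The substitution rows follow from GM_sub = GM_q × (s / GM_q)^(1/n), where GM_q is the geometric mean of the quantifiable values and s is the substituted value:

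- n = 20: 505.3 × (0.5/505.3)^(1/20) = 505.3 × 0.708 = 357.6, which is 29% below the quantifiable-only figure.
- n = 200: 466.0 × (0.5/466.0)^(1/200) = 466.0 × 0.966 = 450.3, which is 3% below it.

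**3. How likely an affected cell is.** With a per-sample BLQ probability p, treating samples as independent, P(at least one) = 1 − (1 − p)ⁿ. The rate p is assumed. The cell sizes are the planned arm size ("It is planned to enroll a total of 480 participants (240 participants within each treatment arm"), that size after the 22.5% dropout assumed in SAP 3.3 (240 × 0.775 = 186), and a smaller cell of 100.

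| p (assumed) | n = 240 | n = 186 | n = 100 |
|---|---|---|---|
| 0.2% | 38% | 31% | 18% |
| 0.5% | 70% | 61% | 39% |
| 1% | 91% | 85% | 63% |
| 2% | 99% | 98% | 87% |

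For example, at n = 240 and p = 0.2%: 1 − 0.998²⁴⁰ = 1 − 0.618 = 0.382.

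**The case against.** Four points can be made for the plan.

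*The display rule may catch the case.* It does not cure it. If the rule covers the geometric mean, a cell with 199 of 200 quantifiable values would be shown as BLQ. If it covers only the arithmetic mean, the geometric mean stays zero or missing. The rule does mean that a printed zero is only one possible outcome. A reader might infer that the plan will report an exposure of zero, or will quietly drop the zeros and overstate exposure. The documents support neither as the outcome, because they do not determine what would be printed. SAP 9.1.1 also lists every concentration by participant, visit and timepoint, so BLQ samples could be traced, although the summary table would not count them.

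*BLQ values should be rare.* This stands in part. Sampling 1-2 hours after dosing, with none in participants off drug, makes them uncommon. It does not exclude them. SAP 8.3 expects some compliance below 80%, SAP 8.4 gives a half-life of 10-12 hours, and the rule also applies to the metabolite, whose levels could be low. Mis-supplied capsules are a narrower route: under SAP 4.1.5 a participant with pridopidine in 10% or less of doses is grouped as placebo.

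*Zero is a legitimate convention.* It is, for the arithmetic statistics, which remain usable.

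*Later PK documents may settle it.* SAP Sections 1 and 9.1.1 leave further PK detail to an addendum or separate SAPs, which are not among the documents reviewed. They may contain a convention, but the current text applies the zero rule to the geometric mean.

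**Conclusion.** The point holds as a conditional one. In any cell with at least one value below the LLOQ, the rule as written makes the geometric mean, and any log-based CV, zero or not computable, and the display clause does not repair this. The algebra needs no assumption. How often it happens cannot be said, since the documents give neither the LLOQ nor a BLQ rate; the probabilities above only show that a low rate could be enough in a cell of planned size.

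The consequence is small. Plasma concentration is an exploratory endpoint and this table is descriptive. The primary analysis, the testing hierarchy, power and the arithmetic PK statistics are unaffected. A reader might infer that the trial's exposure findings or exposure-response work are compromised. The documents do not support that: SAP 9.1.1 makes exposure-response analysis optional and separately reported, and does not apply the zero rule to it. Nor does anything in the documents make LLOQ/2 the required remedy; in a small cell it can lower the figure considerably.

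**What to change.** In SAP 9.1.1, or in the PK addendum that it already allows for:

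- Limit the zero rule to the arithmetic summaries.
- For the geometric mean and any geometric CV, state one convention in advance, for example quantifiable values only, or a named substitution such as LLOQ/2.
- Show the number of BLQ values in each cell.
- Say which mean the BLQ display rule covers, and whether the CV is arithmetic or geometric.

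The cost is a few lines of text and one extra row in the table, with no new data. The downside is that in small cells the figure depends on the convention chosen (505.3 against 357.6 in the assumed n = 20 example), so the BLQ count must stand beside it. If unblinding has already taken place, SAP Section 5 sends the change to the CSR's section on changes to planned analyses.

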9.1.2. Biomarker (NfL) Analysis

Biomarker assessments include:

- Change from Baseline to Weeks 26, 52, 65 and 78 in plasma NfL protein
- Relationship between Baseline NfL and changes from Baseline in select efficacy endpoints
- Relationship between changes from Baseline to Weeks 26, 52, 65 and 78 in NfL and select efficacy endpoints for pridopidine 45 mg bid vs. placebo

- Proportion of participants with stabilization or improvement in change from Baseline to Weeks 26, 52, 65 and 78 in plasma NfL protein

Objectives of the NfL analysis

- (1) To investigate the effect of pridopidine 45 mg bid vs. placebo on changes in log-transformed plasma NfL from Baseline to Weeks 26, 52, 65 and 78 (as pg/mL, with \log_2 transformation), accounting for the effects of Baseline NfL and other possible factors as listed below.

The main analysis is based on change from Baseline in $\log_2(\text{NfL})$ over time, and similar analysis will be repeated for actual values of \log_2 -transformed plasma NfL levels. Analysis will be performed on observed data using MMRM separately for actual values and change from Baseline over time. The model will include the following fixed effects: *treatment*, *categorical weeks*, *Baseline $\log_2(\text{NfL})$* , *Age and BMI at Baseline*, randomization stratification factors (*HD stage and neuroleptic use at Baseline*), interaction effect of *treatment*categorical weeks*. The spatial power covariance matrix for repeated observations within participants will be used. The denominator degrees of freedom for the tests of fixed effects will be approximated by Kenward-Roger method.

Each fixed effect will be tested at a type I error level ≤ 0.05 , two-sided and the 95% two-sided confidence intervals (CI) of the parameters will be computed. The LSMS of actual values and change from Baseline in $\log_2(\text{NfL})$ and associated SE for each treatment group, as well as the LSM, 95% CI, and p-value for the treatment difference (pridopidine 45 mg bid vs. placebo) will be presented at all visits in analysis. The LSM of change from Baseline in $\log_2(\text{NfL})$ at each visit will be back transformed to the percent change in NfL as $2^{\text{LSM}} \times 100 - 100$. The 95% CI of the LSM will also be back transformed.

In addition, actual values, change from Baseline to each visit of $\log_2(\text{NfL})$ and actual value, and % change from Baseline in raw NfL value will be summarized using descriptive statistics and graphics where applicable.

To investigate the additional covariates that may have an effect on change in NfL over time, more covariates will also be added one at a time or altogether to the above model: CAG repeats, age, sex, CAP score, BMI, region, Baseline UHDRS-TFC, Baseline cUHDRS, Baseline Q-Motor [REDACTED] Baseline UHDRS-TMS, Baseline SDMT, and Baseline SWR. When all covariates are added to the model together, a stepwise model selection approach (specifically, a variable needs to be significant at the level of 0.25 to enter the model during the first forwardstep and to be significant at the level of 0.10 to remain in during the second backwardstep) will be adopted in order to see the most influential covariates on the change in NfL over time. Each covariate will be tested at a type I error level ≤ 0.05 , two-sided and the 95% two-sided CIs of the effect estimates will be computed.

- (2) To investigate how Baseline NfL, as a covariate, impacts change from Baseline to Weeks 26, 52, 65 and 78 in efficacy endpoints including UHDRS-TFC, cUHDRS, Q-Motor [REDACTED], UHDRS-TMS, SDMT, and SWR accounting for the effect of pridopidine 45 mg bid vs placebo.

The main analysis is based on the change from Baseline in UHDRS-TFC, cUHDRS, Q-Motor [REDACTED] UHDRS-TMS, SDMT and SWR over time. Each dependent

variable will be fit by one model. Similar analyses will be repeated for actual values of the endpoints.

Analysis will be performed on observed data using MMRM separately for actual values and change from Baseline. The model will include the following effects: *treatment*, *categorical weeks*, *Baseline value of efficacy endpoint to be analyzed*, *Baseline log₂(NfL)*, randomization stratification factors (*HD stage* and *neuroleptic use at Baseline*), interaction effects of *treatment*categorical weeks*, and *treatment*Baseline log₂(NfL)*. The spatial power covariance matrix for repeated observations within participants will be used. The denominator degrees of freedom for the tests of fixed effects will be approximated by Kenward-Roger method.

Baseline log₂(NfL) and its interaction with other factors will be tested at a type I error level ≤ 0.05 , two-sided and the 95% two-sided CI of the parameters will be computed.

The LSM and the associated SE of the Baseline NfL-adjusted efficacy endpoint at some specified Baseline NfL values (such as median, first quartile [low level], and third quartile [high level]) for each treatment group, and the LSM, 95% CI and p-value for the treatment difference (pridopidine 45 mg bid vs. placebo) will be presented for all visits.

To investigate the additional covariates that may have an effect on the efficacy endpoints, more covariates will also be added one at a time or altogether to above model: CAG repeats, age, sex, CAP score, BMI, region. When all covariates are added to the model together, a stepwise model selection approach, as described in Objective (1), will be adopted to see the most influential covariates on the change in NfL over time. Each covariate will be tested at a type I error level ≤ 0.05 , two-sided and the 95% two-sided CIs of the parameters will be computed.

(3) To investigate the relationship between change in NfL over time and change in clinical efficacy endpoints including UHDRS-TFC, cUHDRS, Q-Motor [REDACTED], UHDRS-TMS, SDMT and SWR accounting for the effect of pridopidine 45 mg bid vs placebo.

The dependent variables investigated are clinical outcomes such as UHDRS-TFC, cUHDRS, Q-Motor [REDACTED] UHDRS-TMS, SDMT and SWR over time, with one dependent variable fit at a time.

The main analysis is based on change from baseline in both efficacy endpoints and $\log_2(\text{NfL})$, and similar analyses will be repeated for actual values of efficacy endpoints and $\log_2(\text{NfL})$. Analysis will be performed on observed data using MMRM separately for actual values and change from Baseline over time. The model for change from Baseline in a specific efficacy endpoint over time will include the following effects: *treatment*, *categorical weeks*, *Baseline value of efficacy endpoint to be analyzed*, randomization stratification factors (*HD stage* and *neuroleptic use at Baseline*), *change from Baseline in log₂(NfL)*, interaction effects of *treatment*categorical weeks*, *treatment*change from Baseline in log₂(NfL)*. The spatial power covariance matrix for repeated observations within participants will be used. The denominator degrees of freedom for the tests of fixed effects will be approximated by Kenward-Roger method.

The effect of *change from Baseline in log₂(NfL)* by treatment group will be tested at a type I error level ≤ 0.05 , two-sided and the 95% two-sided CI of the parameter will be computed.

Another simpler approach to perform a simple linear model on the change from Baseline of these clinical outcomes at the specified timepoint may be performed. For Week 65 analysis, the model will include the following effects: *treatment*, Baseline $\log_2(NfL)$, $\log_2(NfL)$ at Weeks 26, 52 and 65, and interaction effects of *treatment** $\log_2(NfL)$ at Baseline and Weeks 26, 52 and 65. Each covariate related to $\log_2(NfL)$ will be tested at a type I error level ≤ 0.05 , two-sided and the 95% two-sided CI of the parameters will be computed.

To investigate the additional possible covariates that can have an effect on change in efficacy endpoints over time, more covariates will also be added one at a time or altogether to the above model: CAG repeats, age, CAP score, BMI, region. When all covariates are added to the model together, a stepwise model selection approach, as described in Objective (1), will be adopted to see the most influential covariates on the change in NfL over time. Each covariate will be tested at a type I error level ≤ 0.05 , two-sided and the 95% two-sided CI of the parameters will be computed.

(4) To investigate the proportion of participants with no increase from Baseline to Weeks 26, 52, 65 and 78 in plasma NfL levels. Other thresholds may also be explored.

The dependent variable is a binary variable which is defined as follows:

$$\text{Dependent variable} = \begin{cases} 1 & \text{if Change from Baseline in } \log_2(NfL) \leq 0 \\ 0 & \text{otherwise} \end{cases}$$

This binary variable dichotomizes changes from Baseline in $\log_2(NfL)$ over time to show whether or not there is a beneficial decrease in $\log_2(NfL)$ from Baseline. Analysis will be performed on the binary data at each visit using logistic regression model. In this model, the log odds of the dependent variable are modelled.

The model will include the following fixed effects: *treatment*, Baseline $\log_2(NfL)$, randomization stratification factors (*HD stage and neuroleptic use at Baseline*), interaction effect of *treatment***Baseline log₂(NfL)*.

Each fixed effect will be tested at a type I error level ≤ 0.05 , two-sided, and the 95% two-sided confidence intervals (CI) of the parameters will be computed. Odds Ratios of treatment effect with their 95% CI at each visit will be presented in analysis.

Subgroup analysis which divides the participants by median Baseline NfL level will be performed for above objectives where applicable.

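### SAP 9.1.2 applies an ordinary 0.05 test and 95% CI to covariates picked stepwise from the same data; for a retained noise covariate that test is positive about half the time

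*SAP*

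**What the plan says.** SAP 9.1.2 Objective (1) fits a repeated-measures model to change in log2(NfL) and then adds further covariates, either singly or all together. In the second case selection is stepwise: "a variable needs to be significant at the level of 0.25 to enter the model during the first forwardstep". A backward pass then drops any covariate that misses the 0.10 level. The stated aim is "in order to see the most influential covariates on the change in NfL over time". The next sentence reads "Each covariate will be tested at a type I error level ≤ 0.05 , two-sided and the 95% two-sided CIs of the effect estimates", and these intervals are to be computed. It covers both routes, singly and stepwise.

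The Objective (1) list begins "CAG repeats, age, sex, CAP score, BMI, region, Baseline UHDRS-TFC, Baseline cUHDRS, Baseline Q-Motor" and goes on to baseline TMS, SDMT and SWR, which makes 12 names. Two of them are already fixed effects in the base model ("Age and BMI at Baseline"), so 10 are new.

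Objectives (2) and (3) take efficacy endpoints as outcomes and reuse the method: "a stepwise model selection approach, as described in Objective (1), will be adopted". They repeat the 0.05 and 95% CI sentence in nearly the same words, with 6 and 5 listed covariates.

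The section has no hold-out sample, no resampling and no selection-adjusted inference. It does not call these p-values and intervals nominal or descriptive.

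**The concern.** The stepwise step uses the p-value twice: once to decide whether a covariate stays, and again to judge it. A covariate in the final model has already passed a 0.10 filter on the same data. Its p-value is therefore no longer uniform under the null, and an ordinary 95% CI around its estimate no longer has 95% coverage.

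This matters because of what the reader will see. The output of a stepwise fit is the set of retained covariates. The relevant error rate for someone reading that table is the one given retention, and that is not the rate the sentence states. A noise covariate could be reported as an influential predictor of NfL or of a clinical endpoint, with an interval that sits away from zero.

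**Working it through.** **Inputs.** Entry 0.25, stay 0.10, test 0.05 two-sided, CI 95%, and 10 new candidates with the base terms forced in (all SAP 9.1.2). Planned sample size 480 (SAP 3.3). CAP is age × (CAG − 33.66) (SAP 7.3.2). cUHDRS is a linear combination of TFC, TMS, SDMT and SWR (SAP 12.1.3).

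**Step 1: the rate given retention.** For a null covariate the final p-value is roughly uniform, and the covariate is kept only if p < 0.10. So

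P(p < 0.05 | retained) = 0.05 / 0.10 = 0.50.

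The 95% CI covers zero exactly when p ≥ 0.05, so coverage given retention = 1 − 0.50 = 0.50. The entry level drops out of this approximation because the stay level is the stricter filter.

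**Step 2: simulation.** 2,500 datasets per row, n = 480, every candidate null. The base terms (treatment, baseline NfL, age, BMI, HD stage, neuroleptic use) were always in the model. Ordinary least squares on one outcome per participant stood in for the repeated-measures model. The SAP's description can be read as a full forward pass followed by a backward pass, or as classical stepwise; both were run. Candidates were either independent or correlated under an assumed structure, with CAP built from age and CAG and cUHDRS from its components.

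| Candidates, algorithm | Retained per candidate | p < 0.05 given retained | CI covers 0 given retained | Retained and p < 0.05, per candidate | Treatment type I error |
|---|---|---|---|---|---|
| Independent, forward then backward | 10.3% | 51.8% | 48.2% | 5.3% | 5.0% |
| Independent, stepwise | 9.9% | 50.4% | 49.6% | 5.0% | 4.8% |
| Correlated, forward then backward | 9.4% | 58.0% | 42.0% | 5.5% | 5.4% |
| Correlated, stepwise | 8.4% | 56.7% | 43.3% | 4.8% | 5.1% |

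The plan's 0.05 is thus reproduced, approximately, as an unconditional rate per candidate (4.8% to 5.5%). It is not reproduced for the covariates that appear in the selected model.

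**Step 3: covariates with a real effect.** Let Z be normal with mean δ (the noncentrality) and variance 1. Coverage given retention is

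P(|Z − δ| < 1.96 and |Z| > 1.645) / P(|Z| > 1.645).

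| δ | P(retained) | Coverage given retained |
|---|---|---|
| 0 | 0.100 | 0.500 |
| 0.5 | 0.142 | 0.712 |
| 1 | 0.264 | 0.890 |
| 2 | 0.639 | 0.961 |

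The shortfall is confined to null and weak effects.

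**Step 4: can all candidates sit in one model?** For Objective (1), no. Baseline cUHDRS is an exact linear combination of baseline TFC, TMS, SDMT and SWR, all of which are listed, so a model holding all five is singular.

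**The case against.** The best defence is that the SAP states a level for each covariate, and that this level holds: across candidates, the chance of being retained and significant is about 5%. The sentence is also unobjectionable for the one-at-a-time models it covers. NfL sits among the exploratory endpoints in SAP 2, and SAP 5.6 waives multiplicity adjustment for other exploratory efficacy endpoints. All of that stands. It does not rescue intervals printed only for covariates that survived a filter, because waiving multiplicity adjustment is a different matter from inference after selection.

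A reader might infer three stronger things, none of which the documents support.

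- That a 5% family-wise level is breached. The simulated chance of at least one false positive per Objective (1) model is 38% to 42%, but the SAP states no family-wise level here. Ten independent tests with no selection give 1 − 0.95^10 = 0.40, so that figure is ordinary multiplicity rather than an effect of stepwise selection.
- That half of all reported covariates are false, or that every interval has 50% coverage. Both 50% figures apply only to covariates that are noise and are retained.
- That the selection could produce false claims about who responds to treatment. The listed candidates are main effects, with no treatment-by-covariate term among them.

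**Conclusion.** Wrong as written, with limited consequences. In the stepwise models of SAP 9.1.2 Objectives (1) to (3), the p-values and 95% CIs of retained covariates do not have the properties stated. For a retained noise covariate, significance occurs about 50% of the time by arithmetic and 50% to 58% in simulation, with coverage of zero between 42% and 50%.

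The arithmetic assumes a roughly uniform null p-value. The simulated range also rests on least squares at one time point in place of the repeated-measures model, and on an assumed correlation structure. The listed covariates are related by construction, so the correlated rows are probably nearer the truth.

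The damage stops at the covariate findings. Type I error for treatment stayed at 4.8% to 5.4% in the simulation, and neither the primary analysis nor the testing hierarchy uses this procedure.

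**What to change.** In SAP 9.1.2 Objectives (1) to (3):

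1. Limit the sentence on the 0.05 level and 95% CIs to models fitted without selection.
2. Report the stepwise output only as a descriptive list of selected covariates, without p-values or intervals.
3. Take covariate estimates, CIs and p-values, labelled nominal, from the one-at-a-time models already planned. Show every candidate, not only the significant ones, or selection returns by another route.
4. If a joint model is wanted for Objective (1), fix its covariates in advance, leave out cUHDRS or one of its four components, and note that age and BMI are already in the base model.

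The cost is a change of wording: no new data, and no new model unless the joint one is chosen. The price is a less definite exploratory output. The one-at-a-time estimates are adjusted for the base-model terms but not for each other, and the stepwise list carries no formal inference.
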